For symptomatic patients, diagnosis is confirmed only after isolation of *Lm* from a normally sterile site, such as blood or spinal fluid (in the setting of nervous system involvement), or amniotic fluid/placenta (in the setting of pregnancy). Stool samples are of limited use and are not recommended. *Listeria monocytogenes* can be isolated readily on routine media, but care must be taken to distinguish this organism from other Gram-positive rods, particularly diphtheroids. Selective enrichment media improve rates of isolation from contaminated specimens. You can expect that the cultures will take approximately 1-2 days for growth. Importantly, a negative culture does not rule out infection in the presence of strong clinical suspicion. Serological tests are unreliable, and not recommended at the present time [36].

Listeriosis is treated with a wide range of antibiotics. In preclinical studies, *wt-Lm* and ADXS31-142 are susceptible to the lowest tested concentration of the following antimicrobial agents:

5.6.1.10 *Management and Surveillance of Listeria during Study Participation*

A subject who experiences a fever (CTCAE Grade 1 or greater) 24 hours following the completion of ADXS31-142 infusion should be started on NSAIDS, hydration and other appropriate measures to treat the fever. In the event that the fever persists or worsens 48 hours following the completion of ADXS31-142 infusion, then oral or broad spectrum IV antibiotics should be considered based on the subject's medical condition. If the fever remains unresponsive to oral/IV antibiotics 72 hours following the completion of the infusion, then a blood culture should be obtained to evaluate for listeremia and determine the appropriate treatment course for the subject. An infectious disease consult should be obtained for further management of these subjects.

All subjects will receive a 6-month course of an oral antibiotic regimen as a prophylactic measure following the completion of the last dose of ADXS31-142 treatment or at the time of study discontinuation. This additional safety measure is intended to eradicate *Lm* from the body. It is expected that a subject will participate in the study until the completion of the full 3-year *Lm* Surveillance Monitoring period. However, following the completion of the 6-month oral antibiotic treatment, a subject will be eligible to participate in other investigational clinical studies.

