Lm Surveillance Monitoring will also be initiated following the completion of the last dose of ADXS31-142 treatment or at the time of study discontinuation. This monitoring will include obtaining a blood sample for CBC, comprehensive metabolic panel (CMP), including C-reactive protein (CRP) and Erythrocyte Sedimentation Rate (ESR), and blood cultures for the detection of listeria. Testing will be performed on all subjects who have received at least one dose of ADXS31-142 and occurs every 3 months (± 2 weeks) for 3 years beginning 3 months after the last dose of study treatment.

Should a diagnosis of listeriosis be made at any point after treatment with ADXS31-142 and the 6-month course of oral antibiotics is completed, immediate and intensive IV antibiotic treatment (ampicillin +/- gentamycin or other IV antibiotic regimen as indicated) is required. An infectious disease consult should be obtained. Based on each individual subject's case and at the discretion of the treating physician, the removal of any foreign medical object that has been present since treatment with ADXS31-142 was initiated may be warranted. It is extremely important that the Investigator, his/her research staff, other healthcare providers involved in the care of the subject as well as each subject participating in this study are educated and made aware of the signs and symptoms of listeriosis and the potential for delayed listeremia/listeriosis. Educational materials for the Investigator, research staff, health care providers and subjects will be prepared, and educational training performed.

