5.7 Subject Study Participation

Each subject may participate in the study for up to 5 years from the time informed consent is signed through the final study contact. This includes a study treatment phase (approximately 24 months), and a 3-year post-ADXS31-142 treatment *Lm* Surveillance Monitoring period. It is expected that a subject will participate in the study until the completion of the full 3-year *Lm* Surveillance Monitoring period. However, following the completion of the 6-month oral antibiotic treatment, subjects will be eligible to participate in other investigational clinical studies.

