8. Study treatment may be administered [REDACTED] of each scheduled infusion. However, ADXS31-142 should not be administered less than 2 weeks apart without Sponsor approval.
9. All subjects will receive a 7-day course of oral antibiotic therapy starting 72 hours after each ADXS31-142 infusion. All subjects will also receive an additional 6-month oral antibiotic course to be initiated 72 hours following the last dose of study treatment or upon discontinuation (See Section 7.1.5.3).
10. AEs and SAEs will be assessed from the time Informed Consent through the completion of the *Lm* Surveillance Monitoring period. All AE/SAEs will be followed through resolution. All AEs/SAEs experienced during this period must be recorded on the eCRF.
11. Monitor vital signs (including weight) pre-dose for all infusions. Vital signs will be checked prior to pembrolizumab (MK-3475) administration, prior to the ADXS31-142 infusion and every [REDACTED] for the first [REDACTED] following the completion of the ADXS31-142 infusion. Weight will be collected once at every visit. Height will be measured at screening only.
12. Thyroid function tests will be monitored only during combination therapy.
13. *Lm* Surveillance Monitoring will include routine monitoring of CBC (excluding LDH), CMP (including CRP, ESR) and blood cultures. All testing will be performed every 3 months (\pm 2 weeks) for 3 years beginning 3 months after the subject's last dose of study treatment or at the time of study discontinuation. During the 6-month post-treatment antibiotic period, AEs that occur, which are deemed by the Investigator to be related to *Lm* or antibiotic treatment, along with the concomitant medications used to treat the AE(s) will be recorded on the eCRF.
14. CT/MRI of the abdomen/pelvis and bone scan. Repeat every 10 weeks (\pm 1 week) during the first cycle and every 12 weeks (\pm 1 week) during treatment. Evaluation should continue every 12 weeks (\pm 1 week) for subjects who discontinue treatment for reasons other than progression.
15. [REDACTED]
16. [REDACTED]
17. [REDACTED]
18. [REDACTED]

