7.1.5.3 Post-Treatment Visits

End-of-Therapy is not a visit; assessments noted in [Section 6](#) must be completed upon the decision to discontinue a subject from study treatment.

Safety follow-up will be conducted via a telephone call at 30 days (\pm 5 days) and 90 days (\pm 5 days) for SAEs after the last dose of trial treatment to confirm the resolution of any ongoing events. Additional unscheduled visits may be considered as needed and at the discretion of the investigator.

All subjects will receive a 6-month course of oral trimethoprim/sulfamethoxazole or ampicillin for subjects with sulfa allergy to be initiated approximately 72 hours following the last dose of study treatment or at the time of study discontinuation. The dose of trimethoprim/ sulfamethoxazole consists of either 160 mg trimethoprim/800 mg sulfamethoxazole (DS) tablet administered three times a week or 80 mg trimethoprim/400 mg sulfamethoxazole administered daily. The dose of ampicillin consists of 500 mg four times daily for 6 months. Review the approved product labeling for trimethoprim/sulfamethoxazole and ampicillin, and monitor antibiotic tolerance as dosing adjustments may be necessary. During the 6-month post-treatment antibiotic period, AEs that occur, which are deemed by the Investigator to be related to *Lm* or antibiotic treatment along with the concomitant medications used to treat the AE(s), will be recorded on the eCRF.

Lm Surveillance Monitoring for the detection of *Lm* will be initiated at the completion of study treatment or at the time of study discontinuation, if earlier. The *Lm* Surveillance Monitoring period will consist of obtaining a blood sample to monitor CBC, CMP, including CRP and ESR, and blood cultures at regular intervals. This testing will be performed on all subjects who have received at least one dose of ADXS31-142. It will occur every 3 months (\pm 2 weeks) for 3 years beginning 3 months after the last dose of study treatment.

During the 3-year *Lm* Surveillance Monitoring period, if a persistent increase in CRP and/or ESR is observed with negative blood cultures for listeria during this time the subject should be evaluated and treated, as appropriate, for another possible cause. In the event that a definite cause has not been identified then subjects must continue to be

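### Part B gives two different start points for the 6-month Listeria antibiotic course and for surveillance, 21 days apart when Week 10 pembrolizumab is the last dose

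*Combined protocol and SAP*

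**What the plan says.** **Antibiotic course.** Section 5.6.1.10 prescribes a "6-month course of an oral antibiotic regimen as a prophylactic measure following the completion of the last dose of ADXS31-142 treatment", or at study discontinuation. Footnote 9 of the Part B flow chart (Section 6.2) has a "6-month oral antibiotic course to be initiated 72 hours following the last dose of study treatment or upon discontinuation". Section 7.1.5.3 says the course is "to be initiated approximately 72 hours following the last dose of study treatment or at the time of study discontinuation". The flow chart dispenses it at End of Therapy, and Section 7.1.5.3 says the End of Therapy assessments "must be completed upon the decision to discontinue a subject from study treatment".

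**Surveillance.** Section 5.6.1.10 says that Listeria monitoring "will also be initiated following the completion of the last dose of ADXS31-142 treatment" or at study discontinuation. The same paragraph then dates the tests as "beginning 3 months after the last dose of study treatment". Section 5.7 calls the period "a 3-year post-ADXS31-142 treatment" surveillance. Footnote 13 of Section 6.2 counts the tests from the "last dose of study treatment or at the time of study discontinuation". The note to Table 15 and Section 7.1.5.3 also count them from study treatment.

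**The term.** *Study treatment* has no formal definition. Section 5.9 applies it to ADXS31-142 and pembrolizumab together. Sections 5.2.2, 5.2.4 and 5.2.5 sometimes appear to mean ADXS31-142 alone.

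**The concern.** ADXS31-142 is live attenuated Listeria (Sections 4.1.1.1 and 4.2.2.1). Pembrolizumab is an antibody (Section 4.1.1.2). The six-month course is meant to eradicate the organism and the surveillance to detect late infection, so the relevant date for both is the last exposure to ADXS31-142. In Part B that can differ from the last dose of study treatment, because Week 10 is a pembrolizumab-only visit.

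A site working from the flow chart and a site working from Section 5.6.1.10 could therefore start the course on different days for identical subjects. At stake are a possible interval without antibiotic cover, a later first blood culture, and inconsistent dates for the end of the course, after which subjects may enter other investigational studies.

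**Working it through.** **Inputs**
- ADXS31-142: Weeks 1, 4 and 7 of each 12-week cycle (Table 7).
- Pembrolizumab: every 3 weeks, so Weeks 1, 4, 7 and 10 (Table 7; Section 6.2 flow chart).
- Per-infusion antibiotic: 7 days, starting 72 hours after each ADXS31-142 infusion (Section 6.2, footnote 9).
- Six-month course: 72 hours after the anchoring dose (Section 6.2, footnote 9; Section 7.1.5.3).
- Surveillance tests: every 3 months, window ±2 weeks, first test 3 months after the anchor (Section 5.6.1.10).

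The plan gives no figure of its own to reproduce.

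**Distance between the anchors, completed cycle.** Day of Week w = 7(w − 1) + 1.
- Last ADXS31-142, Week 7: 7 × 6 + 1 = day 43.
- Last pembrolizumab, Week 10: 7 × 9 + 1 = day 64.
- Difference: 64 − 43 = 21 days.

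**Antibiotic cover, counted in days after the last ADXS31-142 dose.**
- The 7-day course runs from about day 3 to day 10.
- Anchored to ADXS31-142 plus 72 hours, the six-month course starts on day 3, so cover is continuous.
- Anchored to study treatment, it starts on day 21 + 3 = 24.
- Uncovered interval: 24 − 10 = about 14 days.

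This interval arises only when the Week 7 dose is known in advance to be the last ADXS31-142 dose. An example is a complete response followed by one further cycle (end of Section 2.1.2), if both drugs are given through that cycle. In an unplanned stop after Week 10, the decision itself comes after Week 10, so the antibiotic start differs little under either wording.

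**Dosing windows.** Section 5.2.2 allows 7 days either side of a scheduled Day 1. Assuming this applies to each dose separately, the anchors differ by 21 ± 14 = 7 to 35 days, and the uncovered interval is 14 ± 14 = 0 to 28 days.

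**Surveillance.** Taking 3 months as about 91 days, the first test falls about 91 days after the last ADXS31-142 dose under one anchor and 91 + 21 = about 112 days under the other. The whole schedule moves by 21 days, against a test window of 14 days either side.

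**Where the difference is zero**
- Part A, where ADXS31-142 is the only drug.
- Part B stops before Week 10: both drugs were last given on the same day.
- An on-schedule stop at exactly 24 months (about day 731): Week 7 of cycle 9 is day 7 × 102 + 1 = 715 for both drugs, and the Week 10 dose would fall on 7 × 105 + 1 = day 736. If cycle 9 is finished, the difference is again 736 − 715 = 21 days.

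**The case against.** The strongest reply is that this is loose terminology with one intended anchor. Section 5.2.2 dates the 7-day antibiotic course from each study treatment infusion, where Section 6.2 says ADXS31-142. Sections 5.2.4 and 5.2.5 use the term in the same way for premedication and post-infusion vital signs. This is plausible and limits what can be said about intent. It does not remove the conflict, because Section 5.9 uses the term for both drugs and a site has no definition to settle the matter.

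The discontinuation alternative might also be said to cover the case. Footnote 9 says upon discontinuation, without saying of what, so it can be read to include stopping ADXS31-142. But no section says which trigger governs, and Sections 5.6.1.10 and 7.1.5.3 refer to discontinuation of the study.

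On surveillance, the scheduled test dates all use the same anchor, and a 21-day shift is small in a three-year quarterly programme. The later anchor even extends follow-up. That is fair. What remains is that the test dates do not match the period described in Sections 5.6.1.10 and 5.7.

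A reader might go further and infer that a subject who stops ADXS31-142 for good but stays on pembrolizumab would wait months for the eradication course, at about 3 weeks per further dose. The documents do not support that as an expected outcome. Tables 8 and 9 handle each drug separately and do not say whether the other continues. The only single-drug continuation described is ADXS31-142 alone after a complete response (Section 2.1.2). Pembrolizumab alone is neither authorised nor forbidden, so this case is hypothetical and its frequency cannot be derived.

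**Conclusion.** The inconsistency is real and minor. Part B has conflicting start points for the antibiotic course, and its surveillance period and surveillance test dates follow different anchors. The anchors differ by 21 days when Week 10 pembrolizumab is the last dose, and a planned stop of that kind leaves about 14 days between the two antibiotic courses. These figures assume the literal reading of study treatment and on-schedule dosing; the 14 days also assume that the stop is known in advance. The number of subjects affected cannot be worked out from the documents.

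Other safeguards hold under either reading: the 7-day course after each infusion, examination and blood tests at the Week 10 visit, and a culture for fever that persists after an infusion despite antibiotics.

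**What to change.** - Count from the last ADXS31-142 dose, instead of the last dose of study treatment, at the end of the surveillance paragraph in Section 5.6.1.10, in footnotes 9 and 13 of Section 6.2, in the Table 15 note, and in Section 7.1.5.3.
- Start the six-month course about 72 hours after that dose, or on the decision to stop ADXS31-142 permanently if that comes later, even if End of Therapy has not been reached.
- Section 5.5.2 says anti-infectives should be avoided and excepts only documented infection in that item. Add the protocol-mandated course as an exception.
- The Table 15 note restricts cultures to the surveillance period, outside the main part of the study. Allow surveillance cultures to begin while pembrolizumab continues.

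The cost is protocol wording. The ADXS31-142 dose date is already in the dosing records, and no new type of test is needed. In a few subjects the antibiotics or samples would overlap pembrolizumab treatment. For those whose last dose is Week 10 pembrolizumab, surveillance would end about 3 weeks earlier in calendar time, still with three years of testing.

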5.6.1.11 Nausea/vomiting

Nausea and vomiting should be treated aggressively. In addition to the prophylactic antiemetic therapy subjects receive prior to each infusion, consideration should be given to subsequent administration of antiemetic therapy every 8 hours, as needed according to standard institutional practice. Subjects should also be strongly encouraged to maintain liberal oral fluid intake.

5.6.1.12 Management of Infusion Reactions

While there is some overlap between infusion reaction symptoms and cytokine release symptoms, infusion reaction symptoms typically occur during the infusion, while cytokine release symptoms typically occur after the infusion and are mediated by a different mechanism of action. Signs/symptoms of infusion reactions may include: allergic reaction/hypersensitivity (including drug fever); arthralgia (joint pain); bronchospasm; cough; dizziness; dyspnea (shortness of breath); fatigue (asthenia, lethargy, malaise); headache; hypertension; hypotension; myalgia (muscle pain); nausea; pruritic/itching; rash/ desquamation; rigors/chills; sweating (diaphoresis); tachycardia;

tumor pain (onset or exacerbation of tumor pain due to treatment); urticaria (hives, welts, wheals); and vomiting.

Table 11 provides treatment guidelines for subjects who experience an infusion reaction associated with administration of ADXS31-142 or pembrolizumab (MK-3475).

Table 11 ADXS31-142 or Pembrolizumab (MK-3475) Infusion Reaction Treatment Guidelines

NCI CTCAE Grade	Management										
Grade 1 Mild reaction; infusion interruption not indicated; intervention not indicated	Increase monitoring of vital signs as medically indicated until the subject is deemed medically stable in the opinion of the Investigator.										
Grade 2 Requires infusion interruption but responds promptly to symptomatic treatment (e.g., antihistamines, NSAIDS, narcotics, IV fluids); prophylactic medications indicated for ≤ 24 hrs.	Stop Infusion and monitor symptoms. Additional appropriate medical therapy may include but is not limited to: 

IV fluids	Antihistamines	

NSAIDS	Acetaminophen	

Narcotics		

 Increase monitoring of vital signs as medically indicated until the subject is deemed medically stable in the opinion of the Investigator. If symptoms resolve within one hour of stopping drug infusion, the infusion may be restarted at 50% of the original infusion rate. Otherwise dosing will be held until symptoms resolve and the subject should be premedicated for the next scheduled dose. Pembrolizumab (MK-3475) Related: Subjects who develop Grade 2 toxicity despite adequate premedication should be permanently discontinued from further trial treatment administration.	IV fluids	Antihistamines	NSAIDS	Acetaminophen	Narcotics					
IV fluids	Antihistamines										
NSAIDS	Acetaminophen										
Narcotics											
Grade 3: Prolonged (e.g., not rapidly responsive to symptomatic medication and/or brief interruption of infusion); recurrence of symptoms following initial improvement; hospitalization indicated for other clinical sequelae (e.g., renal impairment, pulmonary infiltrates)	Stop Infusion. Additional appropriate medical therapy may include but is not limited to: 

IV fluids	NSAIDS	

Antihistamines	Acetaminophen	

Narcotics	Oxygen	

Pressors	Corticosteroids	

Epinephrine		

 Increase monitoring of vital signs as medically indicated until the subject is deemed medically stable in the opinion of the Investigator. Hospitalization may be indicated.	IV fluids	NSAIDS	Antihistamines	Acetaminophen	Narcotics	Oxygen	Pressors	Corticosteroids	Epinephrine	
IV fluids	NSAIDS										
Antihistamines	Acetaminophen										
Narcotics	Oxygen										
Pressors	Corticosteroids										
Epinephrine											
Grade 4: Life-threatening; pressor or ventilatory support indicated	Subjects who experience a Grade 4 reaction should be permanently discontinued from treatment. Subjects who experience a grade 3 reaction may be discontinued. Discussion with the Sponsor is recommended. Pembrolizumab (MK-3475) Related: If Grade 3 or Grade 4 infusion reaction to pembrolizumab (MK-3475), subject is permanently discontinued from further pembrolizumab (MK-3475) trial treatment administration										

5.6.2 Diet

Subjects should maintain a normal diet unless modifications are required to manage an AE such as diarrhea, nausea or vomiting.

5.6.3 Use in Pregnancy

If a male subject impregnates his female partner, the study personnel at the site must be informed immediately and the pregnancy reported to the Sponsor, and followed as described in [Section 7.2.2](#).

5.7 Subject Study Participation

Each subject may participate in the study for up to 5 years from the time informed consent is signed through the final study contact. This includes a study treatment phase (approximately 24 months), and a 3-year post-ADXS31-142 treatment *Lm* Surveillance Monitoring period. It is expected that a subject will participate in the study until the completion of the full 3-year *Lm* Surveillance Monitoring period. However, following the completion of the 6-month oral antibiotic treatment, subjects will be eligible to participate in other investigational clinical studies.

5.8 Major and Minor Surgeries and ADXS31-142 Treatment

No formal studies of the effect of ADXS31-142 on wound healing have been conducted. However, based on its mechanism of action it is not expected that administration of ADXS31-142 would complicate wound healing. Therefore, a subject may initiate or resume study treatment 2 weeks after minor surgery (i.e., surgery involving little risk to the life of the subject; specifically, an operation on the superficial structures of the body or a manipulative procedure that does not involve a serious risk) if the wound has completely healed and there are no wound healing complications. A subject who has wound healing complications following minor surgery, received major surgery or requires new implants and/or devices (permitted by the protocol) during the course of the study, must wait a minimum of 6 weeks and must have recovered from any toxicity (e.g., return to baseline or Grade 1) and/or complication before the next infusion of study treatment. Sponsor consultation is required prior to resuming study treatment for these subjects. If the treatment is delayed due to concomitant surgery beyond 12 weeks, the subject may be discontinued from the study.

